The research personnel will then conduct a standardized interview to obtain baseline demographic, clinical, and contact information from the parent/guardian (see Enrollment Questionnaire).

The enrolled patient will then be randomized by the Pharmacy Investigational Drug Services. Patients will either receive azithromycin suspension or indistinguishable placebo suspension once daily for three days at a dose of 10 mg/kg/dose with a maximum dose of 500 mg/dose. All research personnel, medical staff, patients, and parents/guardians will be blinded to the composition of suspension prepared in the research pharmacy. If the patient is discharged before the third dose of medication is administered, the pharmacy will provide any remaining suspension doses to be completed by patient as an outpatient.

The selection of the intervention dose of azithromycin (once daily dosing of 10 mg/kg/dose with a maximum dose of 500 mg) was made for several reasons. This dosing is shorter and more convenient to administer than the more commonly used 5 day course with 10 mg/kg/day for one day and 5 mg/kg/day for subsequent days. Since the average length of stay for patients 4-12 years old with asthma is 3 days, it is more likely that patients will complete this dosing during hospitalization. This dosing is currently recommended for other infectious indications including otitis media in penicillin allergic patients. In addition, this dosing is consistent with an open trial registered at clinicaltrials.gov in Denmark studying azithromycin treatment in children 1-3 years of age with recurrent asthma (planned enrollment November 2010 until November 2014).

At the time of enrollment, the patient will have an asthma severity score performed by research personnel via the Pediatric Asthma Severity Score (PASS), which has been validated in children 1-18 years old.^{37,38} The score will be conducted within 30 minutes prior a scheduled beta-agonist treatment or at any time if patient is on continuous albuterol. This score will be used to determine severity of the patient's asthma exacerbation at the time of enrollment.

Pediatric Asthma Severity Scoring (PASS)

Signs	0	1	2
Wheezing (= expiratory sounds heard auscultation)	None/mild	Moderate	Severe or absent due to poor air entry
Respiratory work (= utilization of accessory muscles or retractions)	None/mild	Moderate	Severe

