The primary outcome measure is hospital length of stay (LOS). Preliminary data obtained from a Clinical Looking Glass search reveals that in 2011, there were 410 children between the ages of 4-12 years admitted to CHAM with a primary diagnosis of asthma. During their admission, 237 patients received inhaled steroids, a marker of a persistent asthma diagnosis. Using this data, the mean length of stay was 3.0 days, median 2.5 days, and standard deviation 1.6. The distribution approximated normal distribution in this group. A clinically significant difference in length of stay would be 16 hours or 0.67 days (equivalent to 0.4 standard deviations).

Data analysis will be conducted with the assistance of a statistician. LOS between the two groups will be compared using independent samples t-test, if the data is normally distributed. If the data is not normally distributed, log transformation will be attempted and if the results of the transformation yield normal distribution for both groups, then t-test will be used for the logged values and reported as a geometric mean. If log transformation is not successful in yielding normal distribution, non-parametric Mann-Whitney U test will be used to report median and interquartile ranges. All tests will be two-tailed with an $\alpha = 0.05$ to denote clinical significance.

In order determine the number of patients needed to enroll to detect a 16 hour (0.67 day) difference in length of stay with a power of 80%, PASS software was utilized, with the assistance of a statistician, to model various types of adjustments for non-parametric distribution –normal distribution adjustment, uniform distribution adjustment, and logistic distribution adjustment. For each of these adjustments, the number of patients required for enrollment per

group ranged from 83 to 96 patients. Using the largest number, 96, and assuming a 10% attrition rate for parent/guardian preference, attending preference, or safety exit criteria, the sample size will need to be 107 patients in each group. We anticipate it will take approximately 15-18 months to enroll this number of patients.

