The data from the interview questionnaire will be coded and descriptive statistics will be used to analyze the baseline characteristics of the two groups. If the parent characteristics are not balanced, multi-variable analysis will be utilized to adjust for variables not balanced by randomization. Secondary outcome measures will be compared using chi-squared test for categorical data and t-test or Mann-Whitney U test for continuous data, with statistical significance considered a p value < 0.05.

Due to the invasive nature of the sample collection in the "Mechanism Subset Study", only 25% of patients are expected to agree to submit to this portion of the study. These patients may not be representative of all patients in each arm of the study and will not be randomized. This subset study will be a pilot and feasibility study for future investigation into the potential mechanism of action of azithromycin in asthma. Data will be analyzed to compare the proportion of positive lab findings in each group using chi-squared analysis. There will not likely be sufficient power to find statistical significance, but the results will be used to estimate the effect size for subsequent study.

ETHICAL CONSIDERATIONS

Risks/Benefits

The potential risks are considered minimal. This study meets the category in the U.S. Department of Health and Human Services Code of Federal Regulations, Part 46, Subpart D (§46.405) for research involving greater than minimal risk but presenting the prospect of direct benefit to the individual subjects. The risks are deemed by the investigators to be justified by the anticipated benefit to the subjects; and the anticipated benefit is at least as favorable to the subjects as that presented by available alternative approaches.

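### Baseline asthma severity (PASS) is scored on every child but enters the length-of-stay analysis only if the arms look unbalanced; adjusting for it in any case would be a low-cost gain in precision of unknown size

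*Combined protocol and SAP*

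**What the plan says.** Here PASS means the severity score, not the sample-size software of the same name. Under Study Design, research personnel score each child at enrolment on three signs, each rated 0 to 2 (total 0 to 6). Of its purpose the plan says "This score will be used to determine severity of the" exacerbation at that time. Outcome Measures lists the score among the items also monitored.

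Under Statistical Analysis, "LOS between the two groups will be compared using independent samples t-test, if the data is normally distributed". If LOS is not normal, the plan moves to a t-test on log LOS, and if that fails, to the Mann-Whitney test. No covariate appears at any step.

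On baseline data: "The data from the interview questionnaire will be coded and descriptive statistics will be used to analyze the baseline characteristics of the two groups". The next sentence holds the only adjustment rule: "If the parent characteristics are not balanced, multi-variable analysis will be utilized to adjust for variables not balanced by randomization". There is no threshold for imbalance, no list of variables and no model. The reference to parents is probably a slip for patients.

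**The concern.** Adjusting for a baseline score that predicts the outcome removes outcome variance whether or not the arms happen to differ on it. A rule that waits for an observed imbalance therefore leaves the score unused in most trials where it would help. The children have already been examined, so that information would be lost for want of a sentence in the plan.

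The order of precedence is also open. The text implies that the unadjusted test is primary, but a reader cannot tell what happens to the headline result if some variable is judged unbalanced.

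**Working it through.** **1. The plan's own sample size.** Inputs from Statistical Analysis: difference 0.67 days, SD 1.6, two-sided alpha 0.05, power 80%.

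- Standardized effect: 0.67/1.6 = 0.419.
- Two-sample t-test (noncentral t): 90.5, so 91 per arm.
- Divided by the Mann-Whitney relative efficiency: uniform, 91/1 = 91; normal, 91/(3/π) = 95.3, so 96; logistic, 91/(π²/9) = 83.0, so 83.
- Attrition: 96/0.90 = 106.7, so 107.

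The stated 83 to 96 and 107 reproduce exactly. Sizing was evidently done for the rank test, so any change must keep that fallback usable.

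**2. Gain from always adjusting, normal LOS.** Let R² be the share of LOS variance explained by PASS. The documents do not give it, so every value below is an assumption. Residual SD = 1.6·√(1−R²). Noncentrality = (0.67/residual SD)·√(96/2), with 2·96−3 = 189 degrees of freedom (190 unadjusted). Approximate 95% CI half-width = 1.973 × residual SD × √(2/96), ignoring the small term for chance imbalance.

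| R² | Residual SD (d) | Power | CI half-width (d) |
|---|---|---|---|
| unadjusted | 1.600 | 82.3% | 0.456 |
| 0 | 1.600 | 82.3% | 0.456 |
| 1% | 1.592 | 82.7% | 0.453 |
| 5% | 1.559 | 84.2% | 0.444 |
| 10% | 1.518 | 86.1% | 0.432 |
| 20% | 1.431 | 89.7% | 0.407 |
| 30% | 1.339 | 93.2% | 0.381 |

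Simulation of 200,000 trials per scenario agrees to within 0.3 points of power. If PASS is unrelated to LOS, the cost in power is at most about 0.2 points.

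**3. What a conditional rule keeps.** Same simulations; the trigger is also an assumption, since the plan states none. At R² = 10%, power is 82.3% unadjusted, 82.7% adjusting only if the arms differ on PASS at p<0.05, and 85.9% always adjusting. The share kept is (82.7−82.3)/(85.9−82.3) = 0.4/3.6, about 11%. Across R² of 5 to 30%:

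| Trigger | Trials in which it fires | Share of power gain kept |
|---|---|---|
| p<0.05 | 5% | 11–12% |
| p<0.10 | 10% | 17–21% |
| p<0.20 | 20% | 30–36% |
| standardized difference >0.25 | 8.5% | 15–19% |
| standardized difference >0.2 | 17% | 27–31% |
| standardized difference >0.1 | 49% | 57–65% |

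Only the loosest trigger keeps more than half.

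**4. Type I error.** With no treatment effect, the unadjusted and always-adjusted tests reject in 4.9 to 5.1% of trials. Mechanical trigger rules reject in 3.6 to 5.1%, so there is no inflation.

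**5. Skewed LOS.** Take LOS as lognormal with mean 3.0 and SD 1.6. Log-scale variance is ln(1+(1.6/3.0)²) = 0.250, and the implied median is 3.0·exp(−0.125) = 2.65, against 2.5 in the plan. A proportional effect lowering the mean to 2.33 is ln(3.0/2.33)/0.500 = 0.505 log SDs, so the unadjusted log t-test already has about 94% power. Simulated power with PASS in the log model is 93.6, 94.7, 95.5, 97.3 and 98.7% at R² of 1, 5, 10, 20 and 30%.

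**6. Missing scores.** If a fraction m lacks PASS and is dropped, the variance of the estimate changes by the factor (1−R²)/(1−m). This equals 1 when m = R²: 5% missing cancels an R² of 5%.

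**The case against.** The strongest reply is that an unadjusted primary test in an adequately sized randomized trial is a legitimate choice, and that the benefit rests wholly on an assumed correlation. Both points stand, which is why this is an improvement and not a defect. There are also documented reasons for a weak correlation. Children on albuterol every 4 hours and those needing ventilation are excluded, which narrows the severity range. Scoring is just before a beta-agonist treatment for most children but at any time for those on continuous albuterol, and eligibility is assessed up to 12 hours after admission. On the other side, the Background reads longer stays in azithromycin recipients (mean 4.5 against 3.2 days) as possibly reflecting greater severity. That makes a prognostic role plausible but does not measure PASS.

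Three stronger readings are tempting and are not supported:

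- *The rule inflates type I error.* Applied mechanically, it does not (step 4). Inflation would require choosing between the two results after seeing them. The wording does not exclude that, but nothing indicates that it is intended.
- *PASS lies outside the balance check, so the whole gain is lost.* The balance sentence refers to interview data, and PASS is an examination score. But the adjustment rule speaks of variables generally, and the enrolment interview collects "baseline demographic, clinical, and contact information". The text does not settle the matter.
- *PASS is scored after treatment starts.* The plan says "The score will be conducted within 30 minutes prior a scheduled beta-agonist treatment" and does not order scoring against dosing. After the interview, "The enrolled patient will then be randomized by the Pharmacy Investigational Drug Services". Yet the mechanism subset's first sample is taken at the scoring visit and is called baseline, as against post-treatment. This suggests, without stating, that scoring comes first.

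**Conclusion.** The point holds as a recommended precision improvement. The planned test is valid, the sample size reproduces, and the power target is met without any change. Prespecified adjustment for PASS would raise power from 82% to between about 83% and 93% over assumed R² of 1 to 30% with normal LOS, and by about 0 to 5 points on 94% with lognormal LOS. The true gain could be near zero. Whatever it is, adjusting only on observed imbalance gives up most of it under all but the loosest trigger examined. These figures assume 96 evaluable children per arm, the plan's SD and difference, a linear relation between PASS and LOS (or log LOS), and complete scores.

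**What to change.** Replace the conditional adjustment sentence in Statistical Analysis with a primary comparison adjusted for baseline PASS (0 to 6) whatever the observed balance:

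- ANCOVA on LOS, or on log LOS under the existing normality steps, with treatment and PASS as terms.
- Where those steps lead to Mann-Whitney, a PASS-stratified or covariate-adjusted rank test.
- Only PASS scores taken before the first study dose count as baseline, and the protocol should state that order.
- Children with no usable score stay in the analysis, by simple baseline imputation or a missing indicator.
- The unadjusted test sequence is reported as a sensitivity analysis.

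Settle this before unblinding, and correct the reference to parent characteristics if patients are meant. Age need not be added, since the documents give no evidence that it predicts LOS in this range. The cost is one degree of freedom for the score (one more if a missing indicator is used) and plan wording; no new data and no more patients are needed.

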Telephone follow-up at one week and one month:

1. Hospital readmission rate
2. Days missed of school for patient
3. Days missed of work for parent/guardian
4. Number of emergency room visits for asthma symptoms since discharge
5. Number of physician office visits for asthma symptoms since discharge
6. Number of recurrences of asthma symptoms since discharge
7. Number of courses of oral steroids since discharge (only at 1 month follow-up)

Also monitored: Respiratory viral panel or rapid viral testing results (if obtained as part of medical care), chest x-ray results (if obtained as part of medical care), medication side effects (diarrhea, abdominal pain, vomiting, flatulence), transfer to intensive care unit, time of wean of beta-agonists (q3h and q4h), and asthma severity (PASS score) at time of enrollment

“Mechanism Subset Study”: A Pilot and Feasibility Study in the subset of patients who consent to sample retrieval:

- Nasopharyngeal aspirate samples on enrollment and at 48 hours – measure a set of select biomarkers associated with inflammation (including IL-8) via Bioluminex or ELISA technology, eosinophil and neutrophil count per high power field, Mycoplasma and Chlamydia PCR

[figure not shown]
- Serum on enrollment and at 48 hours – measure same biomarkers of inflammation as in above aspirate, Mycoplasma and Chlamydia IgM and IgG, Mycoplasma and Chlamydia PCR, absolute neutrophil and eosinophil count

METHODS

Population

The study will include patients between the ages of 4-12 years of age admitted to the pediatric inpatient unit or pediatric intensive care unit at the Children's Hospital at Montefiore (CHAM).

Inclusion Criteria: Patients will be considered for enrollment if 4-12 years of age with an admission diagnosis of asthma and a history of persistent asthma (as defined by National Heart, Lung, and Blood Institute; see below and Eligibility Questionnaire).

Key: Alphabetical order is used when more than one treatment option is listed within either preferred or alternative therapy. ICS, inhaled corticosteroid; LABA, inhaled long-acting beta₂-agonist, LTRA, leukotriene receptor antagonist; SABA, inhaled short-acting beta₂-agonist

Notes:

- The stepwise approach is meant to assist, not replace, the clinical decisionmaking required to meet individual patient needs.
- If alternative treatment is used and response is inadequate, discontinue it and use the preferred treatment before stepping up.

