Prolongation of expiration (= ratio of the length of expiration over inspiration)	Normal/mild prolongation	Moderate prolongation	Severe prolongation

Other than the administration of azithromycin suspension or placebo, the medical treatment of the enrolled patients will be at the discretion of the medical team. The current standard of care for treatment of acute asthma exacerbations in hospitalized children includes inhaled beta-agonists and systemic steroids. The medical team often continues or initiates "controller" asthma medications during the inpatient stay (ie inhaled corticosteroids, leukotriene receptor antagonists). In addition, patients with severe asthma might receive intravenous medications (ie magnesium sulfate, terbutaline, aminophylline). No medical treatments will constitute exclusion from the study. However, invasive or non-invasive mechanical ventilatory support will be part of safety exit criteria.

At 7-10 days and again between 28 and 35 days after discharge, research personnel will contact the parent/guardian of enrolled patient for a follow-up interview. This interview will include questions about recurrence of asthma symptoms, days of work/school missed, hospital readmissions, emergency room visits, pediatrician visits, subsequent steroid courses, and medication side effects.

Mechanism Subset Study: A Pilot and Feasibility Study in a Subset of Patients

After enrollment, and at the time of the PASS asthma severity scoring, research personnel will ask parents/guardians if they would also be willing to participate in a separate subset study involving blood and nasal aspirate samples. If parents/guardians consent, they will be offered compensation for their time and inconvenience (if funding is available). If the parent/guardian is interested, the research personnel will obtain a separate, additional informed consent from the parent/guardian and assent from the child for the "Mechanism Subset Study". At that time, a nasal aspirate sample will be obtained by the research personnel (who will be trained on proper technique prior to the start of study). A blood sample will be obtained as soon as possible. A second sample of both blood and nasal aspirate will be obtained on the calendar day that is 48 hours from the first sample. Two samples will allow for baseline and post-treatment samples to be compared.

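### Each secondary outcome may be called significant at an unadjusted p < 0.05, so across 7 to 13 telephone comparisons a chance finding is likely (about 20-48% under assumed correlations)

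*Combined protocol and SAP*

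**What the plan says.** The Statistical Analysis section of the combined protocol and SAP names hospital length of stay as the primary outcome, and all tests are two-sided at 0.05. For the rest it says: "Secondary outcome measures will be compared using chi-squared test for categorical data", and then "t-test or Mann-Whitney U test for continuous data, with statistical significance considered a p value < 0.05".

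The secondary outcomes are listed in Outcome Measures under the line "Telephone follow-up at one week and one month". There are seven:

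- Items 1-3 are readmission, school days missed and parental work days missed. None states a counting window.
- Items 4-6 are emergency visits, office visits and symptom recurrences. Each is counted from discharge, for example "Number of emergency room visits for asthma symptoms since discharge".
- Item 7 is asked once: "Number of courses of oral steroids since discharge (only at 1 month follow-up").

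Study Design gives the timing of the calls: "At 7-10 days and again between 28 and 35 days after discharge".

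No section ranks the telephone outcomes, chooses between the two calls, adjusts for multiplicity or calls these results exploratory. The pilot and low-power wording in Statistical Analysis covers only the Mechanism Subset Study.

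**The concern.** A rule that declares significance outcome by outcome at 0.05 controls the error of each test but not of the set. With many tests, a drug that does nothing can easily produce at least one result that the plan allows to be called statistically significant, in either direction.

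The two calls add to this. For items 4-6 the one-week count is contained in the one-month count, so the same early events are tested twice. For items 1-3 that is only implied.

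What is at stake is how the secondary results may be read, above all if length of stay shows no difference. The Risks/Benefits section mentions readmission, later visits and steroid courses as possible longer-term benefits, so readers will look at these outcomes. The background reports that 14-30% of children admitted there with acute asthma already receive the drug without evidence of efficacy. An isolated positive secondary result could be taken as support for that practice.

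**Working it through.** **Plan's own figure.** The documents state no familywise error for the secondary outcomes, so there is none to reproduce. The section's calculated figures concern the sample size for length of stay alone.

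**Inputs from the documents.** Seven telephone outcomes, two calls and item 7 at one month only (Outcome Measures). Two-sided tests at 0.05 each (Statistical Analysis).

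**Inputs assumed.** The documents give no correlations. The assumed range is 0 to 0.6 between outcomes and 0.3 to 0.7 between the two calls for one outcome. The correlation across both outcome and call is taken as the product of the two.

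**Step 1: number of tests.** 6 × 2 + 1 = 13 if each call is tested separately; 7 if only the one-month values are tested.

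**Step 2: reference value under independence.** Chance of at least one false positive = 1 − 0.95^k.

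- k = 13: 1 − 0.95^13 = 48.7%
- k = 7: 1 − 0.95^7 = 30.2%

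**Step 3: correlated tests.** Simulation of 13 correlated standard normal statistics, each compared with ±1.96:

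| Between outcomes | Between calls | At least one p < 0.05 |
|---|---|---|
| 0 | 0.3 | 47.8% |
| 0.3 | 0.48 | 42.6% |
| 0.5 | 0.48 | 36.9% |
| 0.6 | 0.7 | about 31% |

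The value 0.48 is √(7/30), the correlation of a 7-day count with the 30-day count that contains it when events occur at a constant rate.

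Outside the assumed range, a common correlation of 0.6 between all 13 tests gives 28.8%, and 0.7 gives about 24%.

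**Step 4: seven one-month tests.** 30.2% at zero correlation between outcomes and about 20% at 0.6.

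**Step 5: check with count data.** Simulated nested week and month counts, 96 per arm with assumed event rates and varying shared frailty, gave 39-46% for the 13 tests.

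**Step 6: price of a formal adjustment.** Holm's first step across seven outcomes is 0.05/7 = 0.0071, with a two-sided critical value of 2.690. An outcome with 80% power at 0.05 has a standardised effect of 1.960 + 0.842 = 2.802. Its power at the first step is Φ(2.802 − 2.690) = Φ(0.112), about 54%.

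**The case against.** The strongest reply is that the trial already has one primary objective, one hypothesis and one primary outcome, and is sized on length of stay alone. Outcomes ranked below a single primary are often left unadjusted, and readers know to treat them with caution. This stands in part: the primary type I error is not touched, and formal adjustment is a choice. But the plan does not leave the secondary outcomes unlabelled. It gives them their own rule, "with statistical significance considered a p value < 0.05", and limits its claims only for the mechanism subset.

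Three further objections stand and are reflected in the figures:

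- **The count of 13 is an inference.** The plan does not say that each call is tested separately. That is the natural reading but not the only one; seven tests is also open, hence the second range.
- **The size rests on assumed correlations.** One relapse can produce a recurrence, an emergency visit, a steroid course and missed days together, so high correlation is plausible and 31% is not a floor.
- **Sparse outcomes may fall short of 5%.** With 96 per arm and assumed event rates of 1-2%, a chi-squared test has a true size of about 1.2-3.8%. An expected count of 13 × 0.05 = 0.65 false positives therefore assumes that every test has exact size.

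A reader might also infer more than the documents support:

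- *That the chance is close to one in two.* The 48.7% figure needs 13 independent tests, which the overlap of the two calls contradicts for items 4-6.
- *That most repeated outcomes are explicitly cumulative.* Only three of the six (items 4-6) are. Item 7 is also counted from discharge but is asked only once.
- *That Risks/Benefits commits the investigators to efficacy claims on these outcomes.* It is an ethics statement of what might benefit participants and says nothing about how p-values will be used.

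**Conclusion.** The point holds. As written, the plan lets any one secondary telephone outcome be declared statistically significant at 0.05, with nothing to limit the error across the set. Under the assumed correlations, a drug with no effect has roughly a 31-48% chance of at least one such result if both calls are tested, and about 20-30% if only the one-month values are. Correlations above the assumed range reduce this, but at a common 0.7 the 13-test figure is still about 24%, nearly five times 5%. Testing the additional monitored items listed after the telephone outcomes would add to the count.

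This does not show that the primary analysis is at fault or that a false claim will be made. It shows that the plan's own rule would permit one too readily.

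**What to change.** In Statistical Analysis, remove the p < 0.05 significance rule for individual secondary outcomes and state instead that:

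1. length of stay is the only confirmatory test;
2. the one-month values of the seven telephone outcomes are the main secondary results;
3. all secondary results, the one-week values and the additional monitored items are exploratory, and are reported as between-group estimates with 95% intervals.

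Since items 1-3 carry no counting window, Outcome Measures should also say whether their one-month values run from discharge.

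This is a few sentences of text, with no extra patients or data collection. The downside is that no single secondary outcome can be declared statistically significant. If the sponsor wants a confirmatory claim on a secondary outcome, Holm adjustment across the seven one-month outcomes is an option and holds the familywise error among them at 5% or less. Its price is power: an outcome with 80% power at 0.05 has about 54% at Holm's first step, and the plan reports no power for any secondary outcome.
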